Background: The overarching goal of this proposal is to contribute to safely increasing TB preventive therapy (TPT) uptake in the context of a new South African policy of universal TB testing at ART initiation. TB is the leading infectious cause of death globally; South Africa has one of the highest incidences of TB worldwide (513 cases/100,000 individuals in 2021).¹ TPT forms a cornerstone of World Health Organization (WHO) and South African TB control guidelines. The Fedisa PreventTB study (R01AI150432) is testing a behavioural economics approach to increase TPT prescribing to people living with HIV (PLHIV) in a cluster-randomized trial in 36 public-sector health facilities in South Africa. In preliminary analyses, we have observed overall TPT delivery reaching 51% of PLHIV (among 52,000 patients assessed). While the study is ongoing, the combined data show a marked year to year increase in TPT prescribing at ART initiation from approximately 23% in 2017 to 69% in 2022. Although receipt of TPT has increased, barriers remain.

In 2023, the South African Department of Health introduced targeted universal TB testing (TUTT) at ART initiation (irrespective of the presence of TB symptoms). Guidelines regarding TPT initiation in the setting of TUTT are conflicting - recommending either (1) delaying TPT initiation for all patients until a negative TB test result is returned² or (2) delaying TPT only for those patients with a positive TB symptom screen.³ The new TUTT approach along with ambiguity in the timing of TPT initiation has the potential to substantially reduce timely TPT initiation – missing the period of highest TB risk. In modelling approaches for TB screening and TPT delivery, we found that waiting for a sputum result could decrease TPT prescribing from the current level to approximately 17-31%.⁴ *A novel alternative is to provide TPT at the time of TB testing to all patients initiating or re-initiating ART (TUTT-PT).* Those who test positive for TB (5-8% of patients) would be promptly contacted and switched to anti-TB treatment. Our model suggests that this strategy could ensure that almost 90% of patients receive TPT and are tested for TB simultaneously. The viability of such an approach depends on demonstrating the safety and effectiveness of TPT for all vs the standard of care. Guiding the optimal implementation strategy for TPT delivery - balancing high-levels of TPT prescribing with rapid diagnosis and treatment initiation for active TB disease - is essential to ensure the continued success of South Africa's TPT program.

The Fedisa PreventTB study has a currently active research platform ideal for comparing these two strategies to optimize TPT delivery. We are proposing a one-year study built onto Fedisa PreventTB to compare the proposed novel approach of universal TPT to the standard approaches to inform further TPT policy and optimize the effectiveness of the Fedisa PreventTB behavioral economics approach in light of the new TB testing approach.

Aims: To pilot test the effectiveness and safety of targeted universal TB testing with simultaneous TPT (TUTT-PT) to increase TPT initiation among PLHIV initiating (or re-initiating) ART and to characterize clinic level implementation determinants among health care workers.

Methods: This non-randomized pilot evaluation is designed to evaluate the safety and effectiveness of universal TB testing with simultaneous TPT provision to people living with HIV initiating or re-initiating ART in South Africa.

1.1 Introduction

1.1.1 HIV and TB in South Africa. South Africa is home to over 7.5 million people living with HIV (PLHIV), more than any other country globally.⁵ In addition, South Africa has one of the highest incidence rates of tuberculosis (TB) worldwide, estimated at 513 cases per 100,000 individuals in 2021.¹ Since first offering antiretroviral therapy (ART) in public-sector care for PLHIV in 2004, the South African National Department of Health (NDoH) has progressively expanded treatment access by raising the CD4 count eligibility threshold until ultimately adopting a universal test-and-treat approach in 2016,⁶ with same-day ART initiation following in 2017.⁷ The use of ART reduces the risk of active TB disease in PLHIV;⁸ however, PLHIV still account for more than half of TB case notifications in South Africa.¹ In addition to the expanded use of ART, the NDOH has also committed to reducing the burden of TB disease among PLHIV through the use of TB preventive therapy (TPT). In numerous clinical trials, TPT has been shown to reduce the risk of active TB disease and shorter intermittent regimens, such as 3 months of once-weekly rifapentine and isoniazid (3HP), have proven to be as effective as 6 or 9 months of daily isoniazid preventive therapy (IPT).^{9–13} In a 2015 systematic review of 10 clinical trials providing IPT to PLHIV, an overall 35% reduction in the risk of TB was observed for patients receiving IPT vs placebo (95% CI: 0.51, 0.84), with an even greater benefit observed for those with documented latent TB infection (RR: 0.48; 95% CI: 0.29, 0.82).¹⁴

1.1.2 The prevalence of subclinical TB disease. In recent years, several studies in high TB-burden settings have evaluated the prevalence and clinical features of asymptomatic, or subclinical, TB using universal TB testing, irrespective of symptom status. In a 2021 review of TB prevalence surveys conducted in 23 countries across Africa and Asia, a median of 50.4% of TB disease identified in population-based surveys was identified as subclinical.¹⁵ Studies have also reported on the prevalence of subclinical TB among PLHIV in South Africa. Among ART-naïve PLHIV tested for TB (without consideration for the presence or absence of symptoms), overall prevalence estimates of TB ranged from approximately 13%-19%.^{16–20} Three studies reported that between 16-23% of confirmed TB cases were asymptomatic at the initial evaluation,^{16–18} while other studies reported asymptomatic TB accounting for as low as 9% and as high as 52% of all TB.^{19,20} Finally, in a study of facility-based targeted universal TB testing in South Africa for people living with HIV, those with a previous TB diagnosis in the preceding two years, and those with contact with a TB patient in the last 12 months, 55% of those who tested positive for TB reported no symptoms at the time of specimen collection.²¹

1.1.3 New approach for universal TB testing is a paradigm shift for South Africa. In the 2023 ART Clinical Guidelines, the South African NDoH called for targeted universal TB testing (TUTT) for people living with HIV as a component of the clinical evaluation for ART and TPT initiation, irrespective of symptom status.³ However, guidelines regarding the timing of TPT initiation are conflicting – recommending either (1) delaying TPT initiation for all patients until a negative TB test result is returned² or (2) delaying TPT only for those patients with a positive TB symptom screen.³ The new TUTT approach along with ambiguity in the timing of TPT initiation has the potential to substantially reduce timely TPT initiation – missing the period of highest TB risk. In modelling approaches for TB screening and TPT delivery, we found that waiting for a sputum result could decrease TPT prescribing from the current level to approximately 17-31%.⁴ A novel alternative is to provide TPT at the time of TB testing to all patients initiating or re-initiating ART (TUTT-PT).

1.1.4 There is a knowledge gap regarding the potential viability, safety, and effectiveness of TUTT-PT for PLHIV initiating ART. Our model suggests that the TUTT-PT strategy of universal TB testing with universal TPT (and switch to anti-TB treatment for those who test positive for TB) could ensure that almost 90% of patients receive TPT and are tested for TB simultaneously. The viability of such an approach, however, depends on demonstrating the safety and effectiveness of TUTT-PT vs the standard of care. Guiding the optimal implementation strategy for TPT delivery - balancing high-levels of TPT prescribing with rapid diagnosis and treatment initiation for active TB disease - is essential to ensure the continued success of South Africa's TPT program.

The Fedisa PreventTB study has a currently active platform to compare these two strategies to continue to optimize TPT delivery. We will conduct a one-year study built into Fedisa PreventTB to compare the novel approach of TUTT-PT to the standard approach to inform further TPT policy and optimize the effectiveness of the Fedisa PreventTB behavioural economics approach to TPT prescribing.

1.2 Study Objectives

The overarching goal of this study is to pilot universal TB testing combined with universal TB preventive treatment initiation among people living with HIV initiating ART in South Africa; we will evaluate the feasibility, infer effectiveness and assess possible adverse events associated with this strategy. We will utilize a mixed-methods design comprising of a non-randomized pilot evaluation and in-depth interviews to achieve our study objectives.

The primary objectives are:

1. To compare the proportion of PLHIV who initiate TPT within 7 days of ART initiation based on same day TPT or not.
2. To compare the proportion of PLHIV who initiate TPT and have a subsequent positive TB test result based on same day TPT or not.
3. To estimate the safety of each TPT initiation approach based on the median time to TB treatment initiation among those who test positive for TB based on same day TPT or not.
4. To understand health care provider experiences with implementation of universal TB testing and TPT provision for PLHIV initiating or re-initiating ART

The secondary objectives are:

1. To estimate the proportion of PLHIV evaluated for ART initiation who are tested for TB within 7 days of ART initiation, stratified by symptom status.
2. To determine the prevalence of active TB disease among PLHIV evaluated for ART initiation, stratified by symptom status.
3. To estimate the median time from ART initiation to TPT initiation
4. To determine the proportion of PLHIV diagnosed with TB who remain on TPT for 7 days or longer.
5. To estimate the prevalence of TB drug resistance at TB treatment initiation, stratified by TPT use at the time of TB diagnosis.
6. To estimate the incidence rate of new TB diagnoses within 6 months of ART initiation

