2.1 Study design

We are proposing a **non-randomized pilot evaluation** of a universal TPT initiation strategy within the context of TUTT implementation for PLHIV initiating or re-initiating ART. Clinics will be assigned to the novel TUTT-PT arm or standard TUTT implementation arm with the primary analysis focused on the proportion initiated on TPT within 7 days of ART start. This study will also assess the rate of new TB diagnoses, TB treatment initiation for those testing positive for TB, the prevalence of TB drug resistance at the time of TB treatment initiation, time to TPT initiation, and provider experiences with TUTT implementation and TPT provision, among others.

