2.4 Clinic selection

Among the 18 public sector health facilities that participated in Fedisa in the [name] district, 5 will be selected to participate in the study from the list of clinics below. Clinics were chosen based on the average number of PLHIV who initiated or re-initiated ART on a monthly basis in 2021 and 2022. In order to ensure we can achieve the required sample size; we will select the larger clinics (on the basis of ART (re-)initiations) for study participation. Among the five selected clinics, two clinics will be assigned to standard TUTT implementation, and three clinics will be assigned to TUTT-PT implementation.

District	Clinic	ART initiations 2021	Mean monthly initiations 2021	ART initiations 2022	Mean monthly initiations 2022
Matlosana	Majara Sephapho	230	19.2	133	14.8
Matlosana	Orkney	207	17.25	130	14.4
Matlosana	Gateway NM Pretorius PHC	201	16.8	104	11.6
Matlosana	Kanana	194	16.2	114	10.4
Matlosana	Alabama	159	13.25	162	13.5
Matlosana	Tsholofelo	146	12.2	118	9.8
Matlosana	Empilisweni	144	12	102	11.2
Matlosana	Khuma	120	10	109	9.1

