2.8 Outcomes and analysis

The primary outcomes are the proportion of PLHIV who initiate TPT within 7 days of ART start and the median time to TB treatment initiation for those who test positive for TB. ART initiators include clients who are ART naïve and those re-initiating ART after a lapse in treatment. Secondary outcomes are included in the table below. TB test results and TPT initiation will be ascertained from study source documents and all available data sources in the clinics, including but not limited to paper files, electronic files (Tier.NET and DHIS2), clinic registers, pharmacy records, and lab test results. Analytic approaches are described in the table below.

Table 1. Outcomes & analysis approach

	Outcomes	Data source	Statistical Test
Primary	Proportion of PLHIV who initiate TPT within 7 days of ART (re-)initiation	Paper files, electronic files, clinic registers, pharmacy records, lab test results	Chi-square
Primary	Proportion of PLHIV who initiate TPT and have a subsequent positive TB test result	Paper files, electronic files, clinic registers, pharmacy records, lab test results	Chi-square
Primary	Healthcare provider experiences with universal TB testing and TPT provision	In-depth interviews	N/A
Primary	Median time to TB treatment initiation for those who test positive for TB	Paper files, electronic files, clinic registers, pharmacy records, lab test results	Kaplan-Meier
Secondary	Proportion of PLHIV evaluated for ART (re-)initiation tested for TB within 7 days of ART start, stratified by TB symptom status	Paper files, electronic files, clinic registers, pharmacy records, lab test results	Chi-square
Secondary	Prevalence of active TB disease among PLHIV evaluated for ART (re-)initiation, stratified by symptom status	Paper files, electronic files, clinic registers, pharmacy records, lab test results	Chi-square
Secondary	Median time from ART initiation to TPT initiation	Paper files, electronic files, clinic registers, pharmacy records, lab test results	Kaplan-Meier
Secondary	Proportion of PLHIV diagnosed with TB who remain on TPT for 7 days or longer	Paper files, electronic files, clinic registers, pharmacy records, lab test results	Chi-square
Secondary	Prevalence of TB drug resistance at TB treatment initiation, stratified by TPT use at the time of TB diagnosis	Paper files, electronic files, clinic registers, pharmacy records, lab test results	Descriptive proportions

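### Primary objectives 1 to 3 group participants by same-day TPT, the design and sample size compare assigned clinic arms, and the analysis section does not say which applies

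*Combined protocol and SAP*

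**What the plan says.** Section 1.2 gives three quantitative primary objectives, all with the same grouping:

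- Objective 1: "To compare the proportion of PLHIV who initiate TPT within 7 days of ART initiation based on same day TPT or not".
- Objective 2: "To compare the proportion of PLHIV who initiate TPT and have a subsequent positive TB test result based on same day TPT or not".
- Objective 3, the safety objective: "the median time to TB treatment initiation among those who test positive for TB based on same day TPT or not". The same sentence also speaks of the safety of each initiation approach, which points to the strategies.

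The design is set out by clinic. Section 2.1 says "Clinics will be assigned to the novel TUTT-PT arm or standard TUTT implementation arm with the primary analysis focused on the proportion initiated on TPT", and section 2.4 says "two clinics will be assigned to standard TUTT implementation, and three clinics will be assigned to TUTT-PT implementation". Section 2.9 sizes the study on 65% under routine TUTT against 80% under TUTT-PT, and has safety monitored by arm.

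The 2.8 text names outcomes but no comparison groups: "The primary outcomes are the proportion of PLHIV who initiate TPT within 7 days of ART start and the median time to TB treatment initiation". Table 1 lists chi-square and Kaplan-Meier, also without groups. The term same day is not defined anywhere.

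**The concern.** Same-day TPT is something a participant receives, not something a clinic is assigned. For objective 1 it is also part of the outcome: a person who starts TPT on the day of ART start has started within 7 days. Grouped that way, the comparison shows a large difference whether or not TUTT-PT changes anything. For objectives 2 and 3, the grouping depends on symptoms, clinical suspicion and whether a test result was awaited, and these are bound up with the TB outcomes being compared.

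At stake is the meaning of every quantitative primary result. An analyst following 1.2 and an analyst following 2.1 and 2.9 would produce very different answers from the same data, and 2.8 does not tell them which to report.

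**Working it through.** **1. What the sample size was built for.** Inputs from 2.9: 65% versus 80%, 80% power, 5% significance (two-sided assumed), design effect about 1.3.

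- n per arm = [1.960·√(2·0.725·0.275) + 0.842·√(0.65·0.35 + 0.80·0.20)]² / 0.15² = 138. Multiplied by 1.3, this is 179.4, so 180.
- With continuity correction, n = 151. Multiplied by 1.3, this is 196.3, so 197, close to the stated 200 per arm.

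The plan's figure is therefore reproduced as an arm comparison. (200 + 200 is 400, not the 450 also stated, and 5% of 400 gives the 20 TB cases quoted, against 22.5 for 450. That mismatch does not affect this point.)

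**2. Is same-day TPT just another name for arm?** No.

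- Standard arm: prescribing follows routine care (2.6). Of the two conflicting guidelines described in 1.1.3, one delays TPT only for symptom-positive clients, so others may start the same day. The model cited there puts prescribing at about 17-31% if sputum results are awaited, yet 2.9 assumes 65%. This suggests that many standard-arm clients are expected not to wait, although 2.9 gives no time window.
- TUTT-PT arm: clients strongly suspected of having TB, or with serious contraindications, are not referred for TPT (2.5), and the assumed rate is 80%, not 100%.

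**3. Objective 1 taken literally, with no strategy effect.** Let r be the share starting within 7 days and s the share starting on the day of ART start. The same-day group scores 100% for any s. The rest score (r − s)/(1 − s). With r = 0.65 in both arms and s assumed equal in both:

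- s = 10%: 0.55/0.90 = 61%.
- s = 40%: 0.25/0.60 = 42%.
- s = 60%: 0.05/0.40 = 12.5%.

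**4. Objective 1 taken literally, at the planned rates.** With 200 per arm, 7-day rates of 65% and 80%, and assumed same-day shares s₀ (standard) and s₁ (TUTT-PT), the not-same-day group scores [(0.65 − s₀) + (0.80 − s₁)] / [(1 − s₀) + (1 − s₁)]:

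- 0% and 70%: 0.75/1.30 = 58%.
- 20% and 70%: 0.55/1.10 = 50%.
- 40% and 70%: 0.35/0.90 = 39%.
- 50% and 75%: 0.20/0.75 = 27%.

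The other group is at 100% each time. The arm difference is 15 points throughout. The documents give none of these same-day shares.

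**5. Objective 2.** The outcome requires both starting TPT and a later positive test. The not-same-day group includes people who never start, who cannot meet it, and people whose TPT waited for a negative result, who can hardly have a later positive baseline result. Most of the contrast is fixed by how the groups are formed.

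**6. Objective 3.** About 20 TB cases would be split by a variable that depends on symptoms and suspicion. Strongly suspected TUTT-PT clients would join the comparison group. Severity can also affect time to TB treatment, but the documents do not establish in which direction.

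**7. Power by arm.** At 200 per arm, the effective n is 200/1.3 = 153.8. Then z = [0.15 − 1.960·√(0.39875/153.8)] / √(0.3875/153.8) = 1.00, which gives 84% power (81% with continuity correction). The arm comparison needs no larger sample.

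**The case against.** The strongest reply is that the plan, read as a whole, compares arms. Section 1.1.4 sets TUTT-PT against the standard approach, 2.1 links clinic assignment and the primary analysis in one sentence, 2.9 states the hypothesis by arm, and objective 3 itself refers to each approach. Section 1.1.3 describes TUTT-PT as TPT given when the TB test is done, so the phrase in 1.2 may be loose shorthand for the strategies. That the literal reading is a tautology is itself evidence that it was not meant. This stands as evidence of intent. It does not remove the contradiction, because 2.8 and Table 1 never name the groups, and step 2 shows that the shorthand does not pick out the arms. A receipt-type grouping is also used deliberately elsewhere: drug resistance is to be split by TPT use at diagnosis.

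The circularity is also conditional. It is exact if same day means the day of ART start, and near-complete, not definitional, if it means the day of TB testing. That is accepted.

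A reader might infer that the time-to-treatment comparison would reflect TB severity and not the strategy at all. The documents do not support that. They show a route for confounding, but no size or direction, and positive cases in both arms are traced, with return to the clinic targeted within 72 hours of sputum collection (2.7 and 6).

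A reader might also infer that the plan must be cut to a single primary effectiveness outcome. That would be a preference. The four primary objectives in 1.2 match the four primary rows of Table 1, and the focus on one outcome in 2.1 does not exclude the others. Only the 2.8 text, with two, is out of line.

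**Conclusion.** Objectives 1 to 3 contradict the arm-based design and sample size, and the analysis section leaves the contradiction open. This goes beyond missing detail: a stated grouping, if followed, gives a wrong result. For objective 1, the same-day group is at 100% whatever the strategy does (given the ART-start meaning of the term), and under no effect the gap runs from about 39 points (100% versus 61%) to 87.5 points (100% versus 12.5%) over assumed same-day shares of 10% to 60%. Objective 2 is near-structural, and objective 3 is confounded in an undetermined direction.

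Two stronger readings go too far. One is that the analysis will be done by treatment received, because 1.2 holds the only grouping rule. Sections 1.1.4, 2.1 and 2.9 point the other way, so that is not shown. The other is to take a single scenario, such as the 73-point gap from assumed shares of 50% and 75% (100% versus 27%), as the size of the problem. The shares are assumptions and the gap moves widely with them. Only the 100% is fixed.

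**What to change.** - In primary objectives 1 to 3, replace the same-day grouping with *by assigned clinic arm (TUTT-PT vs standard TUTT)*.
- State the denominators: all enrolled participants in each arm for objectives 1 and 2, and all TB-positive participants in each arm for objective 3.
- Put the same comparison groups in Table 1.
- If a same-day TPT comparison is kept, label it descriptive and define the term (day of ART start or day of TB testing).
- Separately, bring the 2.8 text, which names two primary outcomes, into line with the four primary objectives in 1.2 and the four primary rows of Table 1.

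The cost is wording in 1.2, 2.8 and Table 1, with no new data and no change in sample size. The change removes the circularity and participant-level selection into TPT. It does not remove confounding between five non-randomised clinics, and section 5 already says that inference from the non-randomised pilot is limited.

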2.5 TUTT-PT (intervention) arm

In the TUTT-PT arm, newly initiating or re-initiating ART clients will be referred by clinic staff after ART initiation to the PHRU study nurse for eligibility screening and enrolment. All TUTT-PT arm participants who provide written informed consent will have sputum collected for TB testing (if sputum was not already collected by the clinic staff) and will receive a clinical evaluation for the presence of TB symptoms (cough, fever, weight loss, night sweats) and serious contraindications for TPT initiation (known liver disease, high alcohol intake (men: >5 drinks/day or >15 drinks/week; women: >4 drinks/day or >8 drinks/week), or strong clinical suspicion of TB disease as evidenced by severity of symptoms, including haemoptysis, or Karnofsky score ≤ 50). PLHIV for whom the study nurse does not have a strong clinical suspicion of TB nor evidence of serious TPT contraindications will be referred to clinic staff for TPT initiation, irrespective of the presence or absence of TB symptoms.

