Secondary	TB incidence rate within 6 months of ART initiation	Paper files, electronic files, clinic registers, pharmacy records, lab test results	Descriptive proportions

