2.9 Sample size justification

We hypothesize that TPT prescribing will be 65% in routine TUTT implementation and 80% in TUTT-PT implementation. Thus, we will enrol 200 PLHIV in TUTT clinics and 200 PLHIV in clinics where they will receive TUTT-PT (450 total) in order to detect this difference with 80% power at a 5% level of significance while accounting for clustering by clinic (a design effect of approximately 1.3). A sample size of 450 will also enable us to identify an estimated 20 new ART clients diagnosed with TB (assuming prevalence of 5%) in order to evaluate time to TB treatment initiation. In addition, throughout study implementation, we will conduct ongoing monitoring of intervention safety, defined as the number of participants diagnosed with TB who remain on TPT after diagnosis by study arm.

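### The TB incidence outcome has no rule separating baseline TB from later TB and no person-time, and primary outcome 2 pools the same two kinds of case

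*Combined protocol and SAP*

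**What the plan says.** Secondary objective 6 (section 1.2) is "To estimate the incidence rate of new TB diagnoses within 6 months of ART initiation". Table 1 (section 2.8) lists it as "TB incidence rate within 6 months of ART initiation" and gives descriptive proportions as the method. Neither place states who is at risk, when the clock starts for a person tested at baseline, or what the denominator is.

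Prevalence is a separate outcome, secondary objective 2: "To determine the prevalence of active TB disease among PLHIV evaluated for ART initiation, stratified by symptom status". No rule says that a case counted there is left out of objective 6.

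Primary outcome 2 in Table 1 is "Proportion of PLHIV who initiate TPT and have a subsequent positive TB test result", compared by chi-square. *Subsequent* is its only time rule; there is no window and no reference to specimen date.

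On timing, section 2.5 says that TUTT-PT clients "will be referred by clinic staff after ART initiation to the PHRU study nurse". Sputum is then collected from every consenting participant unless the clinic has already taken it. In the standard arm (section 2.6), laboratory work follows routine care and precedes referral. Section 6 allows 48 hours for results to return.

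**The concern.** A specimen taken at or just after ART start normally gives a result dated after ART start. A positive result is then, in the plain words of objective 6, a new diagnosis inside the 6-month window. The same person is also a prevalent case under secondary objective 2. Without an exclusion rule, the incidence figure largely restates baseline prevalence. Without person-time, the stated method does not produce a rate at all.

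Baseline testing also differs by arm: all TUTT-PT participants have sputum, while standard-arm testing depends on routine practice. A mixed figure would partly measure testing completeness, and TB missed at baseline could surface later as incident.

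For primary outcome 2, two different events score the same. One is TPT started while active TB was already present, the risk that section 7.2 discusses. The other is TB first detected weeks after TPT was started. The first depends directly on whether TPT precedes the test result; the second need not.

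**Working it through.** **Inputs.** From section 2.9: 200 per arm, prevalence 5%, TPT uptake 80% (TUTT-PT) and 65% (standard). From section 1.1.1: national TB incidence of 513 per 100,000, or 0.513 per 100 person-years (PY), for all persons. From section 1.1.2: an asymptomatic share of TB from 9% to 55%. The documents give no later incidence for people starting ART; 2 and 5 per 100 PY are assumptions. Full follow-up is assumed, and all baseline TB is assumed to be detected.

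**The plan's own count.** 400 × 0.05 = 20, which matches the stated 20 cases. The stated total of 450 would give 22.5. The ratios below do not depend on which total is used.

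**Incidence.** Baseline cases P = 400 × 0.05 = 20, leaving 380 at risk. Later cases L = 380 × (1 − exp(−rT)); person-years = L/r; mixed rate = (P + L)/person-years; inflation = (P + L)/L.

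For r = 0.02 and T = 0.5 years: L = 380 × (1 − exp(−0.01)) = 3.8; person-years = 189; mixed rate = 23.8/189 = 12.6 per 100 PY; inflation = 6.3.

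| True later rate per 100 PY | Later cases, 6 months | Baseline share of cases | Mixed rate per 100 PY | Inflation, 6 months | Inflation, 3 months |
|---|---|---|---|---|---|
| 0.513 | 1.0 | 95% | 11.1 | 21.5 | 42.1 |
| 2 | 3.8 | 84% | 12.6 | 6.3 | 11.6 |
| 5 | 9.4 | 68% | 15.7 | 3.1 | 5.2 |

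The 3-month column is shown because Table 2 (section 4.1) schedules the record review and study completion at about 3 months. At 8% prevalence, the top of the protocol summary's range, the 6-month factors at 2 and 5 per 100 PY are 9.7 and 4.5.

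As a simple proportion, the mixed 6-month figure at 2 per 100 PY is 23.8/400 = 5.9%, close to the 5% prevalence. The later-case proportion is 3.8/380 = 1.0%.

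**Primary outcome 2, TPT with a positive baseline specimen.** This assumes that TPT uptake is independent of TB.
- TUTT-PT: 200 × 0.05 × 0.80 = 8.0. This is an upper figure, because section 2.5 does not refer for TPT those with strong clinical suspicion of TB.
- Standard, clinics that wait for the result: 0.
- Standard, TPT delayed only for symptomatic patients: 200 × 0.05 × 0.65 = 6.5; × 0.09 = 0.6; × 0.55 = 3.6.

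**Primary outcome 2, later TB in TPT users** (5 per 100 PY over 3 months). The risk is 1 − exp(−0.0125) = 0.0124, applied to 190 people per arm without baseline TB.
- TUTT-PT: 190 × 0.80 × 0.0124 = 1.9.
- Standard: 190 × 0.65 × 0.0124 = 1.5.

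**Effect of pooling.** If standard clinics wait, 8.0 vs 0 becomes 9.9 vs 1.5, and the risk difference moves from 4.0 to (9.9 − 1.5)/200 = 4.2 percentage points. With 3.6 standard-arm baseline cases, 8.0 vs 3.6 becomes 9.9 vs 5.1, and the ratio falls from 2.2 to 1.9.

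**The case against.** The plan never says that baseline cases will be counted as incident. *Incidence* and *new* ordinarily exclude prevalent disease, and prevalence has its own outcome, so a careful analyst could exclude them. This stands: the defect is an undefined case definition whose literal reading gives the error. It is not a stated decision to miscount. The pairing of a rate with descriptive proportions is on the page either way.

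A reader might infer that primary outcome 2 hides the hazard of TPT during active TB. The figures do not support that, since the risk difference barely moves. The plan also covers the hazard elsewhere: time to TB treatment, people with TB remaining on TPT for 7 days or longer, resistance by TPT use, and monitoring by arm (sections 2.8 and 2.9).

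A reader might also take 8 vs 0 as the expected contrast. The 8 is an upper figure. The 0 needs standard clinics to wait for results, and the plan's own model then puts TPT prescribing at about 17-31% (section 1.1.3), not the 65% used for later cases above. At 17-31%, later standard-arm cases would be about 0.4 to 0.7 (190 × 0.17 or 0.31 × 0.0124).

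Nor should objective 6 be faulted for failing to show that earlier TPT prevents TB. It only estimates a rate, without an arm comparison, and section 5 accepts limited inference. Finally, not everyone is first tested after ART start: clinics may already have taken sputum, and standard-arm tests precede referral. This limits how many baseline diagnoses fall after ART start; it does not supply the missing rule.

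**Conclusion.** The concern holds as a missing case definition and a method that does not yield the stated quantity. Taken literally, baseline TB would make up most of the incidence numerator: 84% at 2 per 100 PY and 68% at 5, with the 6-month rate about 6 and 3 times too high. These sizes rest on the plan's 5% prevalence, complete detection at baseline, full follow-up and assumed later rates. At the lower national all-person rate the distortion is larger.

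Primary outcome 2 mixes two events whose balance differs between arms. Pooling dilutes the relative contrast and makes the result harder to interpret, but it does not conceal the safety signal. The rule should be settled before analysis, because otherwise it will be chosen once the data are known.

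**What to change.** - Classify each TB case by specimen collection date, with one baseline window for all outcomes. An example is up to 7 days after ART (re-)initiation, which the plan already uses for TB testing. State how far before ART start a specimen still counts.
- For objective 6, exclude baseline cases from the numerator and person-time, start person-time after the window, and report cases per person-year with an exact Poisson interval in place of descriptive proportions.
- Keep primary outcome 2, but report it by arm in two parts: positive on a baseline-window specimen, and first positive on a later specimen. Limiting the first part to specimens taken on or before TPT start would be a poor substitute. It would drop someone who starts TPT on day 0 and has a positive specimen from day 3. Because routine care sets the order in the standard arm, it could undercount exposure there.
- Report participants untested at baseline separately, since missed prevalent TB can appear as incident.
- Confirm that LT001 and MR001 record specimen dates. Table 2 lists laboratory results and TB diagnoses but does not mention collection dates.

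The cost is wording in section 1.2 and Table 1, with no added visits; a date field may be needed. The price is precision. With 4 later cases in 189 PY, the exact 95% limits on the count are 1.09 and 10.24, or about 0.6 to 5.4 per 100 PY. That width reflects what a pilot of this size can say about later TB.
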